32. DRUGS OR DEVICES

Based on the FDA's Policy for Device Software Functions and Mobile Medical Applications (2019), TASCS is unlikely to be subject to regulatory requirements because (1) it resembles examples given under Appendix B for which the FDA intends to exercise enforcement discretion because they pose lower risk to the public and (2) will neither transform a mobile platform into a regulated medical device nor connect to an existing device type for purposes of controlling its operation, function, or energy source (Appendix C). Towards the end of the study period, we will revisit this issue based on the eventual functionality of the TASCS and initiate the 513(g) process as appropriate.

INVESTIGATOR STUDY PLAN - TASCS

Statistical Analysis Plan

STATISTICAL DESIGN AND POWER

In this two-year R34, data will be used primarily to iteratively improve the TASCS and assess feasibility and acceptability of pilot implementation in the emergency department. In Aim 1, we will build the TASCS using input and feedback from empaneled stakeholders. In Aim 2, we will obtain introduce the TASCS to emergency department patients with suicide risk to examine usability and acceptability in vivo. Finally, in Aim 3, we will conduct a pilot feasibility trial with three arms:

- (1) In-person clinician-administered TASCS ED App in the ED followed by telephone coaching calls, facilitated by the Post-ED Clinician App, and access to the Post-ED Patient and Family App
- (2) Telehealth-based TASCS in the ED followed by telephone coaching calls, facilitated by the Post-ED Clinician App, and access to the Post-ED Patient and Family App
- (3) Self-administered TASCS in the ED followed by telephone coaching calls, facilitated by the Post-ED Clinician App, and access to the Post-ED Patient and Family App

Data analyses will proceed with an intent-to-treat approach. Statistical significance will be at $p < .05$ and analyses will occur via IBM® SPSS® Statistics V21 and SAS 9.4 statistical software package (SAS Institute Inc, Cary, NC).

A. Aim 2: Usability Testing. Analyses will center around assessing usability, acceptability, and needs for program updates based on users' experiences. We will apply descriptive statistics to assess participants' comments and questions related to specific program/equipment features and global assessments. Usability outcomes will be: 1) ability to use the program and equipment without staff assistance after training (yes/no), 2) time (in minutes) to complete the TASCS process once trained, and 3) total number of deviations from the direct path of completing TASCS procedures after training. The stopping point for testing will be having three patients rate the platform as having a SUS score of ≥ 80 . We will track and store usage statistics, including time on each page and time in app. Google Analytics will constitute a secondary source of statistics.

B. Aim 3: Feasibility Trial. It is important to note that, being an initial feasibility trial, the study is not powered to find a difference between arms and we are not seeking to compare TASCS to treatment-as-usual to examine effectiveness. Rather we are seeking to describe the usability and acceptability of different modes of delivering TASCS in the ED, of the Post-ED Clinician App, and the Post-ED Patient and Family App, to examine potential intervention targets, and to examine the utility of our chosen measures at baseline and follow-up.

Initial analyses will compare the three treatment groups on baseline demographic and clinical variables using a chi-square test (for categorical variables) and analysis of variance (for continuous variables). Variables that significantly differ between groups or are theoretically important will be used as covariates in multivariate analysis, when appropriate. We will proceed with intent-to-treat analyses. Baseline and three-month usability and acceptability analyses will compare the three treatment groups using analysis of variance. The behavioral outcome in the feasibility trial will be occurrence of any suicidal behavior (attempt, preparatory, aborted or interrupted attempt, death by suicide) and categorical level of ideation during three-month follow-up. Analyses will compare the three arms via chi-square for suicidal behavior and Kruskal-Wallis test for ordinal level of suicidal ideation. Changes in suicidal behavior and suicidal ideation over time will be examined using McNemar (overall) and Friedman tests (by

INVESTIGATOR STUDY PLAN - TASCS

arm) respectively. To elucidate the impact of intervention components on intervention targets, we will use t tests to compare our three main intervention targets at follow-up (social support, behavioral activation, and impulse control) between those who did and did not receive the intervention component specific to that target, and will use t tests to examine the association between intervention targets and patient outcome (occurrence of any suicidal behavior and presence of active suicidal ideation at follow-up). For all analyses, effect sizes will be estimated, with parametric and non-parametric statistics as appropriate.

Sample size justification. For our development and usability testing, we will engage 12 individuals with lived experience for persona testing in Aim 1 and 12 ED patients for in vivo usability testing in Aim 2. This number was chosen because a sample of 10 users can identify 95% of usability problems¹ including in persons with serious mental illness.² The sample size for the feasibility trial (n=45) is based on the same principle, allocating 15 patients in each of the three arms and allowing for moderate attrition over the three-month follow-up period. Because of the funding mechanism and our focus on platform development, the feasibility trial is **not** powered to test hypotheses but rather to inform the feasibility of the intervention and data collection measure for a future large-scale implementation trial. With significance set at 0.05 and assuming a power of 0.80, a sample size of 45 participants across three arms will allow us to detect a large effect size of $f=0.48$ in usability and acceptability scores and $w= 0.46$ in dichotomous suicidal behavior outcome.

REFERENCES

1. Faulkner L. Beyond the five-user assumption: Benefits of increased sample sizes in usability testing. *Behav Res Methods, Instruments, Comput.* 2003;35(3):379-383. doi:10.3758/BF03195514.

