6. INCLUSION AND EXCLUSION CRITERIA*

Inclusion and Exclusion Criteria: See grant: “HUMAN PARTICIPANTS PROTECTION” (p.15) for details. No prisoners will be enrolled (including individuals with ankle monitors) without first obtaining IRB review and approval for this population and without first setting the required prisoner certification in place

For Aim 1, individuals will be eligible to provide input into the development of TASCS if they are aged ≥ 18 years, and have direct, family or clinical experience of suicidality. They will be excluded if they are medically/cognitively unable to participate or are a prisoner.

For Aims 2 and 3, participants will be invited to participate if they own a smartphone and if they meet the following eligibility criteria:

INVESTIGATOR STUDY PLAN - TASCS

Eligibility criteria	
Inclusion Criteria	Exclusion Criteria

 ➤ Age \geq18 years ➤ Presenting to the UMMHC EDs ➤ Screened positive for suicidal ideation in the past 2 weeks or attempt in the past 6 months 	
 ➤ Medically/cognitively unable to participate in screening or assessment (e.g., sustained altered consciousness, psychosis, hostile behavior, intubation, severe pain) ➤ Currently in state custody ➤ Already enrolled during previous visit ➤ No access to reliable telephone for follow-up

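### Covariates can be chosen by significance tests between randomized arms, while the between-arm ideation test cannot use the baseline Columbia level; name that covariate in advance

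*Combined protocol and SAP*

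**What the plan says.** Everything here concerns the Statistical Analysis Plan, section B (Aim 3: Feasibility Trial), unless another place is named.

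- Baseline comparison: "Initial analyses will compare the three treatment groups on baseline demographic and clinical variables using a chi-square test (for categorical variables"), with analysis of variance for continuous ones.
- Covariate rule: "Variables that significantly differ between groups or are theoretically important will be used as covariates in multivariate analysis, when appropriate". The SAP text names no variable and specifies no multivariable model for any outcome.
- Between-arm outcome tests: "Analyses will compare the three arms via chi-square for suicidal behavior and Kruskal-Wallis test for ordinal level of suicidal ideation".
- Change over time: ideation is examined within each arm by the Friedman test.
- Effect sizes: "For all analyses, effect sizes will be estimated, with parametric and non-parametric statistics as appropriate".
- Status of the comparisons: "the study is not powered to find a difference between arms".

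The Aim 3 measures table in protocol section 11 (Procedures Involved) covers baseline and follow-up and includes the Columbia scale. The Friedman test over time also presupposes a baseline ideation level.

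**The concern.** The covariate rule has two routes. The first is a significant difference between randomized arms. Such a difference arises by chance, and its p-value measures imbalance, not how strongly the variable predicts outcome. The second is theoretical importance, which could admit baseline ideation but leaves the choice open.

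Neither route reaches the ideation comparison as written, because Kruskal-Wallis accepts no covariate. The plan uses baseline ideation within arms but not between them.

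At stake is the width of the arm contrasts and their exposure to chance imbalance in baseline ideation. Type I error is not in question. Because effect sizes are promised for every analysis, the precision of those estimates has some value even in an unpowered pilot.

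**Working it through.** **1. The plan's own figures.** Inputs from the SAP sample size justification: N = 45, three arms, α = 0.05, power 0.80, f = 0.48, w = 0.46.

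- ANOVA: noncentrality f²N = 0.48² × 45 = 10.37 on 2 and 42 df; power 0.800.
- Chi-square: w²N = 0.46² × 45 = 9.52 on 2 df; power 0.795.

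Both reproduce. The plan gives f = 0.48 only for an effect "in usability and acceptability scores" and states no detectable effect for ordinal ideation, so its use for ideation below is illustrative.

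**2. How often chance selects a covariate.** With k independent baseline tests at .05, the probability of at least one significant result is 1 − 0.95^k: 23% for k = 5, 40% for k = 10, 64% for k = 20. The SAP does not give k.

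**3. Normal-theory guide to the gain.** With one covariate, the standard error is multiplied by √[(1 − r²)(N − 3)/(N − 4)]. At N = 45:

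- r = 0: √(42/41) = 1.01
- r = .3: √(0.91 × 42/41) = 0.97
- r = .5: √(0.75 × 42/41) = 0.88
- r = .7: √(0.51 × 42/41) = 0.72

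**4. Simulation of the ordinal outcome.** All settings are assumptions:

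- latent bivariate normal baseline and follow-up with correlation r;
- arm means −d, 0, +d with d = f√1.5;
- follow-up cut into six levels (35/15/15/15/10/10%) and baseline into six (5/10/20/25/20/20%);
- 15 per arm and 5,000 trials per setting (simulation SE at most .007).

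Rank ANCOVA regresses the rank of follow-up level on arm and the rank of baseline level.

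| | r = .1 | r = .3 | r = .5 | r = .7 |
|---|---|---|---|---|
| Power, f = 0.48, Kruskal-Wallis | .729 | .741 | .712 | .722 |
| Power, f = 0.48, adjust only if baseline differs at p < .05 | .727 | .742 | .716 | .733 |
| Power, f = 0.48, rank ANCOVA | .731 | .769 | .813 | .910 |
| Power, f = 0.25, Kruskal-Wallis | .246 | .257 | .237 | .248 |
| Power, f = 0.25, rank ANCOVA | .257 | .280 | .295 | .390 |
| Type I error, Kruskal-Wallis | .050 | .048 | .051 | .051 |
| Type I error, rank ANCOVA | .054 | .050 | .050 | .053 |
| CI width in ranks, f = 0.25, unadjusted | 18.19 | 18.17 | 18.21 | 18.21 |
| CI width in ranks, f = 0.25, adjusted | 18.36 | 17.78 | 16.53 | 14.29 |
| Ratio of widths | 1.009 | .978 | .908 | .785 |

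Divided by N = 45, the interval at r = .5 goes from 18.21/45 = .405 to 16.53/45 = .367. A repeat with 3,000 trials per setting gave width ratios of 1.009/.978/.909/.787.

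**5. Attrition.** The plan is "allocating 15 patients in each of the three arms and allowing for moderate attrition over the three-month follow-up period" but gives no rate. With 12 per arm (20% loss assumed) and f = 0.25, the width ratios at r = .3/.5/.7 are .981/.913/.791, practically unchanged.

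**6. Restricted baseline range.** Protocol section 6 enrols patients who "Screened positive for suicidal ideation in the past 2 weeks or attempt in the past 6 months", which probably lowers r. Truncating the latent baseline, with r of .3/.5/.7 before truncation:

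| Enrolled part of the baseline distribution | r among enrolled | Power gain at f = 0.48 (points) | Ratio of CI widths, f = 0.48 |
|---|---|---|---|
| Top 20% | .14/.26/.42 | 1/2/6 | 1.006/.990/.951 |
| Top 50% | .19/.33/.51 | 1/4/9 | 1.001/.974/.915 |

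At f = 0.25 with top-20% truncation the power gain is 1/1/3 points.

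**The case against.** The strongest reply is that this refines a comparison the plan itself disclaims. The trial is a 45-patient feasibility study, it is declared unpowered for arm differences, and Kruskal-Wallis is valid. Even with adjustment, at f = 0.25 and r = .5 the interval is .367 wide, while the contrast between the two extreme arms is only about .16; power stays near .30. That stands, and it is why the point is minor.

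The larger gains are also the less plausible ones, given who is enrolled. That stands too: the r = .7 column should not drive the judgement.

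The simulated significance rule is only half of the written rule, since theoretical importance could admit baseline ideation, and a multivariable analysis could be read as additional to Kruskal-Wallis. This is fair. The row in question shows only that the significance route recovers almost nothing. The other route still names neither variable nor model.

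Protocol sections 10 and 13 refer endpoints and analysis to grant pages that are not among the documents, and a covariate may be named there. The finding is therefore limited to the SAP text.

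Finally, a mean-rank difference divided by N is an unfamiliar scale, and because ranks are pooled over three arms each pairwise contrast depends partly on the third. That is a real cost, met by also tabulating levels by arm.

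**Conclusion.** The concern holds, as a minor point and a cheap improvement. The fault in the covariate rule does not depend on any assumption: a significance test between randomized arms is the wrong way to choose covariates, and the named ideation test could not use one anyway.

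The size of the gain does depend on assumptions, chiefly r among enrolled patients. For r of .3 to .5 the arm-contrast interval narrows by about 2% to 9% at f = 0.25. Under strong restriction of the baseline range the change runs from about 1% wider to 5% narrower. At r = .1 the cost is about 1% in width with practically no change in power. No sample size or detectable effect stated in the SAP is wrong on this account.

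**What to change.** Delete the baseline significance tests and the clause that makes a significant arm difference a ground for adjustment. Show baseline characteristics descriptively by arm. Name any other theoretically important covariate before outcome data are seen, or delete that phrase. Replace the ideation test with:

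> Ideation level during follow-up will be compared between arms by rank ANCOVA: rank of follow-up level on arm plus rank of baseline Columbia ideation level, the only covariate, with an overall F test for arm. Three contrasts (in-person minus telehealth, in-person minus self-administered, telehealth minus self-administered) will be reported as adjusted mean-rank differences divided by the number analysed, each with a 95% confidence interval, without multiplicity adjustment and labelled exploratory. A missing baseline level will be given the overall mean baseline rank. Ideation level will be tabulated by arm, and Kruskal-Wallis will be a sensitivity analysis.

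Leave the usability and acceptability ANOVA, the chi-square test for suicidal behavior and the t tests as they are. Missing follow-up levels are a separate matter that this change does not address.

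The cost is SAP wording, one degree of freedom, and a less familiar effect scale, which the table of levels offsets. No new data are needed.

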11. PROCEDURES INVOLVED*

For **Aim 1**, the design thinking workshops are described in the grant application under “RESEARCH PLAN” (p.9-10).

For **Aim 2**, participants will be recruited from UMMHC EDs. This will include patients (n~12) and their treating physicians or behavioral health clinicians (n~4). See grant: “RESEARCH PLAN” (p.10) for details on the procedure. We will collect the following:

- Patient case report form, for demographics, psychiatric and suicide history, familiarity with mobile phone/computing technology, self-efficacy/capability
- System Usability Scale (SUS)
- User Engagement Scale (UES)

The second half of these participants (Cycle 2) will also be invited to download the app to their smartphone and followed up to obtain these usability measures again one week after ED discharge (“Cycle 2”, RESEARCH PLAN, p.10). Participation will not affect their care, see grant: “HUMAN PARTICIPANTS PROTECTIONS” (p.19-20).

Aim 3 is a pilot randomized controlled trial of 45 ED patients who screened positive during triage for recent active suicidal ideation or suicide attempt. They will be recruited from UMMHC EDs. They will be randomized to one of three TASCS App modalities in the ED (in-person clinician, telehealth clinician, self-directed). All three groups will receive three

INVESTIGATOR STUDY PLAN - TASCS

counseling calls, access to the TASCS app, and one assessment call in the three months after discharge. See grant: “RESEARCH PLAN” (p.11-13) for details on the procedure. Participation will not affect their care see grant: “HUMAN PARTICIPANTS PROTECTIONS” (p.19-20). Measures to be included are:

Measures at baseline and follow-up in feasibility trial (Aim 3)

Construct	Measure
Initial implementation measures	
Usability	System Usability Scale
Acceptability	Qualitative feedback
	Technology Acceptance Model Scale
	User Engagement Scale
Patient-level outcomes	
Suicidal ideation and behavior	Columbia Suicide Severity Rating Scale ;suicide-related ED visits
Intervention targets	
Behavioral activation/effort	Drive subscale of the Behavioral Activation Scale; BH engagement
Perceived social support	Interpersonal Needs Questionnaire; lethal means restriction
Suicide-related impulse control	McCullumsmith et al. (2014)
Implementation outcomes	
Engagement	Session length, number of features used, screens with most user interaction, completeness of templates
Costs	Clinician time spent and associated costs; billability of services

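### The between-arm ideation test (Kruskal-Wallis) leaves baseline ideation unused; name it as covariate with an ordinal model, and label pre-post change as descriptive

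*Combined protocol and SAP*

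**What the plan says.** For the between-arm comparison, SAP section B (Aim 3: Feasibility Trial) reads: "Analyses will compare the three arms via chi-square for suicidal behavior and Kruskal-Wallis test for ordinal level of suicidal ideation". The outcome is the ordinal level of ideation over the three months of follow-up. Protocol section 11 lists the Columbia scale in its table of Aim 3 measures taken at baseline and follow-up, and provides for one assessment call after discharge.

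On covariates, the same SAP section says: "Variables that significantly differ between groups or are theoretically important will be used as covariates in multivariate analysis, when appropriate". On change over time it says: "Changes in suicidal behavior and suicidal ideation over time will be examined using McNemar (overall) and Friedman tests", the Friedman test being run by arm. It adds: "For all analyses, effect sizes will be estimated, with parametric and non-parametric statistics as appropriate". No confidence intervals are mentioned.

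The sample size paragraph describes "allocating 15 patients in each of the three arms and allowing for moderate attrition over the three-month follow-up period", with no attrition figure. Protocol section 6 admits patients who "Screened positive for suicidal ideation in the past 2 weeks or attempt in the past 6 months". All three arms receive the intervention; even the third is "Self-administered TASCS in the ED followed by telephone coaching calls". The SAP sets a general significance level of 0.05. It also says that the trial is not powered to separate the arms and makes no comparison with usual care.

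**The concern.** Baseline ideation will be in hand: the Friedman test cannot be run without it. Yet that test works within each arm and does not compare arms, while the test that does compare arms has no place for it. The covariate sentence does not settle the matter, because it attaches to no named outcome or model and cannot operate inside a Kruskal-Wallis test. With 15 patients per arm or fewer, information that predicts the outcome is set aside.

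A second, smaller matter concerns interpretation. Patients are enrolled because of recent ideation or an attempt, and no arm goes without TASCS. Some fall in ideation and behavior is expected whatever the intervention does. The SAP plans tests of change under the 0.05 rule without saying how to read them. A significant fall could be taken as a sign of benefit when the larger trial is planned.

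**Working it through.** **1. The plan's own figures.** None is given for ideation. The nearest are f = 0.48 (usability and acceptability) and w = 0.46 (suicidal behavior) at N = 45, three arms, alpha 0.05, power 0.80.
- ANOVA, noncentral F with df 2 and 42 and noncentrality N·f²: detectable f = 0.4797.
- Chi-square, df 2, noncentrality N·w²: detectable w = 0.4627; power at 0.46 is 0.795.

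Both reproduce and neither is in dispute.

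**2. What a baseline covariate is worth in principle.** Let ρ be the baseline-to-follow-up correlation, which the documents do not give. Adjustment uses error df 41 and effect f/√(1−ρ²); the equivalent sample is 45/(1−ρ²).

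| ρ | Detectable f, adjusted | Equivalent N |
|---|---|---|
| 0 | 0.480 | 45 |
| 0.3 | 0.458 | 45/0.91 = 49 |
| 0.5 | 0.416 | 45/0.75 = 60 |
| 0.7 | 0.343 | 45/0.51 = 88 |

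**3. Simulated power on an ordinal scale.** All inputs are assumed: normal baseline and follow-up cut into six levels and one arm shifted 0.8 SD (f = 0.8·√2/3 = 0.38). Kruskal-Wallis is tie-corrected; rank ANCOVA is the F test for arm given ranked baseline; 20,000 trials per cell.

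| Setting | Kruskal-Wallis | Rank ANCOVA, ρ = 0.2 / 0.4 / 0.6 |
|---|---|---|
| 15 per arm | 0.52-0.53 | 0.55 / 0.59 / 0.69 |
| 12 per arm (20% attrition) | 0.42 | 0.44 / 0.48 / 0.58 |
| 15 per arm, half of unshifted patients at lowest follow-up level | 0.38-0.39 | 0.40 / 0.43 / 0.50 |

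The gain at 15 per arm is about 2, 6 and 16 points. If entry screening truncates baseline at −0.5 to +0.5 SD, it falls to about 0.5-1, 2-3 and 5-9 points. With a shift of 0.3 SD and no truncation, power is 0.11 against 0.11 / 0.12 / 0.14, a gain of 0, 1 and 3 points. At ρ = 0 with f = 0.48, both tests give 0.76.

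**4. Validity.** With no arm effect, rejection is 0.043-0.050 for Kruskal-Wallis and 0.047-0.054 for rank ANCOVA, across 10, 12 or 15 per arm. The gain is not bought with extra false positives.

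**5. Proportional odds at this size** (1,500 fits, ρ = 0.4). The likelihood-ratio test rejects 6.1% of null trials at 15 per arm and 6.8% at 12. The SD of the log odds ratio at 15 per arm is 0.73, so when two arms do not differ a typical 95% interval is exp(±1.96 × 0.73) = 0.24 to 4.2.

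**6. Pre-post change with no effect.** If entry requires baseline above c, the expected fall is (1−ρ)·φ(c)/(1−Φ(c)) SD. At ρ = 0.5 and entry of the top half, this is 0.5 × 0.399/0.5 = 0.40 SD; for the top 20% it is 0.70 SD. With two occasions the Friedman test is a sign test, (n₊ − n₋)²/(n₊ + n₋). On six levels, with cuts of −0.5 to +0.5 SD and ρ of 0.4 to 0.8, it shows apparent improvement in 7-63% of arms of 15, against a nominal 2.5% in that direction. A repeat simulation gave 7-68%.

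**The case against.** **The covariate sentence already covers this.** It has two triggers, and theoretical importance is one. Baseline ideation plainly qualifies. A reader might infer that adjustment depends on a significant baseline difference; the text does not say so. This part of the objection stands: the SAP shows intent to adjust. What it lacks is the named variable and a model for the ordinal outcome.

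**Kruskal-Wallis is not wrong.** That stands too. A reader might infer that a chance baseline imbalance makes the between-arm result unreliable. Overall error is at or just below 5%. Under entry selection, even in trials whose largest baseline gap is at least 0.5 of the sample's own SD, Kruskal-Wallis rejects in only about 5%, 5-6% and 6-7% at correlations of 0.2, 0.4 and 0.6.

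**Power matters little in this trial.** The SAP says that the trial is not powered for arm differences, and the arms share the same calls and post-discharge app, so differences may be small. This limits the importance of the point. It does not justify discarding a measurement already taken.

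**The pre-post reading is already guarded.** The SAP disclaims effectiveness and promises effect sizes, so a label is a clarification and not the correction of an error. The upper false-improvement rates assume that everyone is selected on ideation, whereas a recent attempt also qualifies.

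**Recall windows.** A reader might infer that the six-month screening window supplies baseline behavior and is set against three months of follow-up. No passage says so, and that claim is not made here.

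**Unseen pages.** Protocol sections 10 and 13 refer to grant pages for endpoints and analysis. A model or label could be there; none is in the documents provided.

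**Conclusion.** The point holds as a minor, inexpensive improvement. The stated between-arm ideation test is valid but leaves scheduled baseline information unused, and the covariate sentence is too general to put it to use. The gain is precision only: about 2 to 16 points of power in the unselected case, about 0.5 to 9 if entry screening narrows the baseline range, nil at zero correlation, and small for small arm differences. These figures rest on assumed values for the correlation, scale, shift and attrition, since the documents give none. The documents do not support a claim that the planned test is biased or that the SAP presents pre-post change as benefit. The descriptive label is worth adding because entry selection alone can produce significant falls.

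**What to change.** In SAP section B (Aim 3):

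1. Name baseline Columbia ideation level as the covariate for the between-arm ideation comparison, whatever the baseline significance tests show.
2. Take the between-arm p-value from rank ANCOVA (ranked follow-up on arm and ranked baseline).
3. Report odds ratios with 95% CIs from a proportional-odds regression of follow-up ideation on arm and baseline ideation. Use it for estimates and not for the p-value, since its likelihood-ratio test is slightly liberal at this size.
4. Report within-arm ideation change (for example percent improved minus percent worsened) and overall behavior change as descriptive, with 95% CIs. State that they include regression to the mean and are not an intervention effect. As an illustration, 9 improved, 3 worsened and 3 unchanged of 15 gives (9 − 3)/15 = +40 points, 95% CI about 0 to 80. Friedman may stay, described as a sign test.

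The cost is SAP wording and one degree of freedom, in the software already named, with no added patients or visits. The odds-ratio intervals will be wide, and two methods are needed for one comparison.

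### The SAP compares suicidal behavior across arms of 15 by plain chi-square with no rule for small counts, so a sparse observed table can carry a p-value on the wrong side of 0.05

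*Combined protocol and SAP*

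**What the plan says.** Section B of the SAP (Aim 3: Feasibility Trial) defines a yes/no outcome over three months. It is met by a suicide attempt, preparatory behavior, an aborted or interrupted attempt, or death by suicide. The between-arm test is named in one sentence: "Analyses will compare the three arms via chi-square for suicidal behavior". The opening section (Statistical Design and Power) sets significance at p < .05.

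The sample size justification describes "allocating 15 patients in each of the three arms", "allowing for moderate attrition over the three-month follow-up period", with no figure for the attrition. It then quotes a detectable effect: "With significance set at 0.05 and assuming a power of 0.80", 45 participants give f=0.48 for usability and acceptability scores and w=0.46 "in dichotomous suicidal behavior outcome".

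The SAP gives no expected rate of suicidal behavior, names no exact test and has no rule for small expected counts. The nearest wording, on using parametric or non-parametric statistics as appropriate, is attached to the estimation of effect sizes and not to the choice of this test. Sections B and the sample size justification both say that the trial is not powered for between-arm comparisons.

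**The concern.** The comparison is a 3x2 table with 15 patients per row. Chi-square without qualification is naturally read as the Pearson statistic referred to its large-sample distribution on 2 degrees of freedom. With few events that reference distribution is a poor guide to how unusual the observed table is, and at this sample size few events are likely over a wide range of rates.

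At stake is a statement that delivery modes differ significantly in suicidal behavior, resting on a handful of events, when an exact calculation from the same table would not support it. The SAP says the pilot is to inform a later large-scale trial, so a p-value for its most serious outcome should not hinge on an approximation that is known to be weak for sparse tables.

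**Working it through.** **Inputs from the SAP.** Three arms, 15 per arm, N=45, alpha 0.05, power 0.80, w=0.46, f=0.48. **Assumed, because the documents give no figure:** the event rate (a range is shown) and attrition (20%, leaving 12 per arm, as an illustration).

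**1. The plan's own figures.** Power for w uses the noncentral chi-square with 2 df and noncentrality N·w². At w=0.46 it is 0.795, and the w that gives exactly 0.80 is 0.463. Power for f=0.48 from the noncentral F on 2 and 42 df is 0.800. Both quoted effect sizes reproduce.

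**2. When expected counts are small.** With m events in total, each arm's expected count is m/3, which is below 5 when m ≤ 14. That is fewer than 15 of 45 (33%), or fewer than 15 of 36 (42%) with 12 per arm. The binomial probability of m ≤ 14 is:

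| Assumed event rate | 45 followed | 36 followed |
|---|---|---|
| 15% | 0.998 | >0.999 |
| 20% | 0.975 | 0.998 |
| 25% | 0.867 | 0.979 |
| 30% | 0.635 | 0.908 |
| 40% | 0.143 | 0.518 |

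**3. Events 0/0/3, 15 per arm.** The expected count is 1 event and 14 non-events per arm. The squared deviations sum to 1+1+4=6, so X² = 6/1 + 6/14 = 6.429. On 2 df, p = exp(−6.429/2) = 0.040. The Fisher-Freeman-Halton p-value adds the probabilities of all tables with the same margins that are no more likely than the observed one. Here these are the three orderings of 0/0/3: 3·C(15,3)/C(45,3) = 1365/14190 = 0.096.

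**4. Events 0/1/4, 12 per arm.** The expected count is 1.667 events and 10.333 non-events. The squared deviations sum to 8.667, so X² = 8.667·(1/1.667 + 1/10.333) = 6.039 and p = 0.049. The exact tail is six orderings of 0/1/4 (6·12·495 = 35640) plus three of 0/0/5 (3·792 = 2376): 38016/C(36,5) = 38016/376992 = 0.101.

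**5. Other patterns.** Full enumeration at 15 per arm finds further disagreements at 0.05 with fewer than 15 events, including 0/2/5 (0.040 against 0.052) and 2/3/8 (0.035 against 0.070). In every disagreement chi-square is significant and the exact test is not.

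**6. Long-run error with no arm difference.**

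| Event rate, 15 per arm | Chi-square size | Exact size |
|---|---|---|
| 5% | 0.024 | 0.004 |
| 10% | 0.035 | 0.015 |
| 20% | 0.043 | 0.032 |
| 30% | 0.052 | 0.040 |

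The chi-square maximum is about 0.052 at 15 per arm and about 0.061 at 12. Conditional on exactly 3 events in total it is 0.096, the highest for any total at 15 per arm.

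**7. Power cost of the exact test.** For true risks 0, 0 and x, w² = 2x/(3−x). Setting this to 0.46² = 0.2116 gives x = 0.287. With 15 per arm, chi-square rejects at 3 or more events in the third arm and the exact test at 4 or more. The binomial tails are 0.850 and 0.664.

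**The case against.** The strongest reply is that the long-run behavior of chi-square is acceptable here. At 15 per arm its size stays near or below 0.05 and is closer to nominal than that of the exact test, so preferring a conditional exact test is partly a matter of school. The trial also disclaims power for arm differences twice, aims mainly to describe usability and acceptability, and will report effect sizes for all analyses, so the p-value would not stand alone.

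Much of this stands, and it rules out several stronger readings.

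- **Inflated type I error.** A reader might infer this from the 0/0/3 example, but the enumeration does not show it. That table is the worst case, and with no arm difference its probability (in any order) is only about 2% at most. The two tests reach identical decisions at many totals, for example at 4, 5, 6, 8, 9 and 10 events.
- **Expected counts certain to be below 5.** This needs an event rate that the documents do not give. The composite is broad and the patients are selected for recent ideation or attempt, so rates of 25% to 30% or more cannot be excluded.
- **Any three events in one arm are significant.** Only if the other two arms have none: at 15 per arm, 0/1/3 gives p=0.147 and even 0/1/4 gives 0.054.
- **The w=0.46 is wrong.** It reproduces. Risks of 0%, 0% and 29% are only its least favorable configuration; at 5%, 25% and 55% (w=0.456) the exact test has power 0.81.
- **A delivery mode would be dropped, or the baseline tables are equally affected.** Nothing in the documents ties an arm p-value to a decision on modes, and no baseline calculation supports the second claim.

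What does not stand is that a disclaimer of power answers the point. Low power concerns missed differences. The SAP still sets a threshold and names this test, and a p-value of 0.040 for a table whose exact value is 0.096 overstates the evidence whatever the power.

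**Conclusion.** The point holds as a specification gap of modest size. The SAP names chi-square for a comparison in which expected counts per arm are very likely to be below 5 if the event rate is about 20% or lower, and more likely than not at 30%. It provides no alternative for that case. The consequence is confined to the p-value of a sparse observed table, which can be about half the exact value and cross 0.05 (0.040 against 0.096; 0.049 against 0.101).

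The conclusion rests on reading chi-square as the large-sample Pearson test, on assumed event rates, and on an assumed 20% attrition for the 12-per-arm figures. The protocol also refers to a grant research plan (its section 13) that is not part of these documents, so a rule stated only there could not be checked.

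**What to change.** State in section B of the SAP that the three-arm comparison of suicidal behavior will use the Fisher-Freeman-Halton exact test when any expected count is below 5, and that event counts and denominators will be reported for each arm. The expected counts depend only on the table margins, so the rule can be fixed in advance. A mid-p version would not serve: for 0/0/3 it gives half of 0.096, that is 0.048, and leaves the verdict unchanged.

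The cost is one sentence, with no change to design or data collection. The downside is that the exact test is conservative and loses power, for example 0.66 against 0.85 at true risks of 0%, 0% and 29% with 15 per arm. That is a small price in a trial that disclaims power for arm differences. The w=0.46 can stay, as long as it is understood to describe the chi-square test.
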